5.4 Definition of Dose-Limiting Toxicity

Toxicities will be graded in severity according to the guidelines outlined in the NCI-CTCAE version 4.0. Dose limiting CNS and non-CNS (hematologic and non-hematologic) toxicities will be defined differently and will be based on events that occur during the study period. In order to be declared as dose-limiting toxicity, an adverse event must be related (definite, probable, or possible) to study treatment.

A dose-limiting toxicity (DLT) will be defined as any one of the following adverse events occurring within 8 weeks from last dose of radiation therapy:

CNS toxicities:

Acute CNS toxicities (occurring \leq 30 days after completing FSRT treatment):

• Any grade 3 or higher central nervous adverse events including but not limited to headache, dizziness, vertigo, new onset seizures, cerebral edema, cerebral hemorrhage, and new onset neurologic deficit.

Delayed onset CNS toxicities (occurring >30 days after completing FSRT treatment):

 Any grade 3 or 4 adverse event arising within the irradiated volume including but not limited to radiation necrosis or focal neurological deficits.

Non-CNS toxicities:

Non-hematologic toxicities:

- Any grade 3 or higher non-hematologic adverse event with the exception of alopecia, fatigue, and anorexia.
- Grade 3 or higher nausea and/or vomiting that persists ≥ 48 hours despite optimal medical management.

Hematologic toxicities:

- Grade 4 neutropenia lasting for \geq 7 days in duration
- Grade \geq 3 febrile neutropenia with/without infection

• Grade 4 thrombocytopenia

Dose escalation will be determined based on the occurrence of DLTs. For the purposes of determining whether to advance the dose levels, DLTs will be counted by patient. In the event of the development of any grade 3 or 4 toxicity felt to be at least possibly related to study drug, TPI 287 will be held until resolution to grade 1 or baseline assuming that occurs within 15 day window.

Dose escalation will follow the standard 3+3 design. The enrollment to next higher dose level will be delayed for 8 weeks after the completion of FSRT by the last patient enrolled at the dose level. This period of 8 weeks will allow monitoring potential delayed toxicities. Management and dose modifications associated with the above adverse events are outlined in Section 6. Dose escalation will proceed according to the following scheme. Dose-limiting toxicity (DLT) is defined above.

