Number of Patients with DLT at a Given Dose Level	Escalation Decision Rule
0 out of 3	Enter 3 patients at the next dose level.
≥2	Dose escalation will be stopped. This dose level will be declared the maximally administered dose (highest dose administered). Three (3) additional patients will be entered at the next lowest dose level if only 3 patients were treated previously at that dose.
1 out of 3 or ≥ 2 grade 2 CNS toxicities	 Enter at least 3 more patients at this dose level. If 0 of these 3 patients experience DLT, proceed to the next dose level. If 1 or more of this group suffer DLT, then dose escalation is stopped, and this dose is declared the maximally administered dose. Three (3) additional patients will be entered at the next lowest dose level if only 3 patients were treated previously at that dose.
≤1 out of 6 at highest dose level below the maximally administered dose	This is the dose to be used in the expanded cohort and will be considered recommended phase 2 dose. At least 6 patients must be entered at this dose.

Table 2. Dose Escalation Rules

If dose level 1 is found to cause unacceptable toxicity, the dose will be de-escalated to level -1 (7 mg/m^2). Three patients will be enrolled at dose level -1. If no DLT is observed, three additional patients will be enrolled at dose level -1 such that safety is established in at least 6 patients prior to entering dose expansion phase.

Any delayed CNS-toxicity arising within the radiation field but seen beyond the window for DLT registration (> 8weeks following completion of FSRT) will be recorded. Furthermore, occurrence of any delayed-onset treatment related grade 3 or higher central nervous toxicity at any time (during and after DLT period of 8 weeks) will lead to holding dose-escalation and adding 3 patients to the dose level at which toxicity has occurred. Occurrence of additional delayed-onset treatment related grade 3 or higher CNS- toxicity will be reviewed with Protocol Monitoring Committee and IRB to determine whether discontinuation or modification of trial is subsequently warranted.

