5.5 General Concomitant Medication and Supportive Care Guidelines

Because there is a potential for interaction of TPI 287 with other concomitantly administered drugs through the cytochrome P450 system, the use of drugs or herbal supplements that are known to be strong inhibitors/inducers of CYP3A4 and CYP2C8 are not permitted (Appendix B).

Prophylactic use of corticosteroids is allowed during the study to limit symptoms from metastases or radiation.

Non-enzyme inducing anti-epileptic drugs may be utilized to control or prevent seizures.

Principal Investigator should be alerted if the patient is taking any agent known to affect or with the potential to affect selected CYP450 isoenzymes.

5.6 **Duration of Therapy**

Patients will receive TPI 287 on days 1, 8, and 15 (total of 3 doses). On day 1, the TPI 287 will be administered 4 (+/-2) hours prior to FSRT.

5.7 **Duration of Follow Up**

Patients will be seen in follow-up on the 3rd, 6th, 9th, 12th, 15th, and 18th month following the first day of treatment with TPI 287. Patients will be followed for 18 months after first treatment on study or until death, whichever occurs first.

The following will be obtained at pre-treatment evaluation and at each follow up visit: Symptoms history, vital signs/ height and weight, physical examination, KPS/ECOG score, Mini-Mental State Examination, steroid use, quality of life questionnaire, and toxicity evaluation.

Radiologic assessment, MRI brain with and without gadolinium, will be performed at pretreatment and every three months following the end of treatment until the patient is off-study or reaches the 18 month study completion date.

Furthermore, the principal investigator will have close collaboration with oncologists treating the systemic malignancy. Information regarding the status of systemic malignancy such as results of standard imaging evaluations, serum biomarkers measurements, and systemic treatments will be collected and recorded at each visit.

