5.8 Criteria for Removal from Study

Patients will be removed from study when any of the below criteria applies:

- Disease progression requiring therapy not allowed in the protocol, including whole brain radiation.
- Intercurrent illness that prevents further administration of treatment: a condition, injury, or disease unrelated to cancer, that renders TPI 287 or radiation treatment unsafe or regular study visits impossible, including, but not limited to, active infection, symptomatic congestive heart failure, unstable angina pectoris, cardiac arrhythmia, pregnancy, or psychiatric illness that would limit compliance with study requirements.
- Unacceptable adverse event(s) (see adverse events)
- Patient decides to withdraw from the study
- General or specific changes in the patient's condition that render the patient ineligible for the study
- Non-compliance with study treatment or protocol-required evaluations and study visits
- Inability of subject to comply with study requirements
- Determination by the investigator that it is no longer safe for the patient to continue therapy
- Patient who inadvertently becomes pregnant (see reporting of pregnancy)

Patients may withdraw at any time or be dropped from the study at the discretion of investigator should any untoward effects occur. In addition, a patient may be withdrawn by the investigator if he/she violates the study plan or for administrative and/or other safety reasons. The investigator or study coordinator must notify Cortice Biosciences immediately when a patient has been discontinued/withdrawn due to a serious adverse experience. All trial treatment-related toxicities and SAEs at the time of discontinuation/withdrawal should be followed until resolution or stabilization. Patients who are discontinued from the study will still be followed for disease progression.

All deaths that occur within the trial period or within 30 days after administration of the last dose of trial drug must be reported to Cortice Biosciences for the purposes of serious adverse event (SAE) reporting; however, deaths due to progression are not SAEs.

Patients who discontinue from the study for reasons unrelated to the study (e.g., personal

reasons, or adverse events after registration but prior to receiving study therapy) may be replaced as required for the study to meet its objective. The replacement will generally receive the same treatment or treatment sequence (as appropriate) as the allocation number replaced.

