10. STUDY CALENDAR

Baseline evaluations are to be conducted within 1 week prior to start of protocol therapy. MRI scans must be done ≤ 2 weeks prior to the start of therapy. In the event that the patient's condition is deteriorating, laboratory evaluations should be repeated within 48 hours prior to initiation of the next cycle of therapy.

	Baseline Concurrent phase		Single agent phase		Final [†]	Follow up ^g
		D1	D8	D15		
TPI-287 infusion		Х	Х	Х		
XRT ^a		Х				
Informed Consent	X					
History and Con-meds	Х	х	Х	Х	Х	Х
Baseline Symptoms ^b	X					
Performance status (Karnofsky performance status/ECOG)	Х	Х	Х	Х	Х	Х
Physical Examination (including neurological assessment)	Х	Х	Х	Х	Х	Х
Vital signs and Height/Weight	X	Х	Х	Х	Х	Х
Documenting status of systemic disease	X	X	Х	Х	Х	X
Adverse event evaluation		Х	Х	Х	Х	Х
Quality of life assessment (QLQ-BN20 and QLQ-C15-PAL)	X	X	Х	Х	Х	X
Steroid use assessment	Х	Х	X	Х	X	Х
Blood ^c	Х	Х	Х	Х	Х	
B-HCG	Х					
Radiological assessment ^d	Х					Х
PK samples ^e			X			
Mini-Mental State Examination	Х	Х	Х	Х	Х	X
Lumbar puncture			Х			

^a Radiotherapy will be delivered once daily Monday through Friday, D1-5 for a total of 5 treatments.

^b Baseline symptoms include symptoms occurring on D1 prior to receiving TPI 287 and within 1 week prior.

^c Blood will include CBC and differential, sodium, potassium, chloride, creatinine, AST, ALT, bilirubin, ALP, albumin, calcium, magnesium, phosphate.

^d Radiologic assessment, MRI brain with and without gadolinium, will be performed at pre-treatment and every three months following the end of treatment until the patient is off-study or reaches the 18 month study completion date.

^e PK samples (blood and CSF) will be collected on D8.

^fA final visit will be performed approximately 30 days following completion of treatment with FSRT and/or TPI-287 (whichever treatment occurs last).

^g Information pertaining to survival and long term assessment of the subject's disease status and adverse events will be collected approximately every 12 weeks beginning after the final visit for period of up to 18 months.

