11.1 Antitumor Effect

Definitions

Evaluable for toxicity. All patients will be evaluable for toxicity from the time of their first treatment with TPI 287.

Evaluable for objective response. Only those patients who have received at least one dose of TPI 287 concurrent with FSRT, and have had their disease re-evaluated will be considered evaluable for response. These patients will have their response classified according to the definitions stated below.

Methods for Evaluation

All measurements should be taken and recorded in metric notation using a ruler or calipers. All baseline evaluations should be performed as closely as possible to the beginning of treatment and never more than 2 weeks before the beginning of the treatment.

The same method of assessment and the same technique should be used to characterize each identified and reported lesion at baseline and during follow-up.

Evaluation of Target Lesions

Complete Response (CR): The tumor is no longer seen on two sequential MRI scans, and the patient is on no steroids or only adrenal-maintenance dose of steroids.

Partial Response (PR): \geq 50% decrease in the product of two diameters of target lesions on two sequential MRIs, taking as reference the baseline product of two diameters, provided that the patient has not had his/her dose of steroids increased since the last evaluation period.

Minor Response (MR): Decrease in diameter products of < 50% on two sequential MRI scans provided that the patient has not had his/her dose of steroids increased since the last evaluation.

Stable Disease (SD): The scan shows no change, taking as reference the smallest product of diameters while on study. Patient should be receiving stable or decreasing doses of steroids.

Progressive Disease (PD): > 25% increase in the product of two diameters of target lesions; taking as reference the smallest product on study (this includes the baseline product if that is the smallest on study), provided that the patient has not had his/her dose of steroids decreased since the last evaluation period. A concomitant decrease in steroid dose will rule out a progression designation at this point. The appearance of one or more new lesions is also considered progressions.

Furthermore, the response will be also measured with RANO working group criteria for metastatic brain tumors when this guideline is published.

Duration of Response

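### No rule requires a patient counted as DLT-free to have been observed to the end of the 8-week window, and no visit is scheduled in its last 16 days

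*Combined protocol and SAP*

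**What the plan says.** **Window and count.** Section 5.4 defines a DLT as a qualifying related event within 8 weeks of the last radiation dose. It adds: "For the purposes of determining whether to advance the dose levels, DLTs will be counted by patient". CNS events more than 30 days after FSRT have their own delayed-onset definition. Enrolment to the next level waits 8 weeks after the last enrolled patient completes FSRT, and the stated purpose is: "This period of 8 weeks will allow monitoring potential delayed toxicities".

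**Denominator.** Table 2 (5.4) gives its decision rules as counts out of 3 or out of 6. Its accrual instructions speak of patients *entered* or *treated*; for the recommended dose, "At least 6 patients must be entered at this dose". For level -1, the text after the table asks that safety be established in at least 6 patients.

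**Evaluability.** Section 11.1 says: "All patients will be evaluable for toxicity from the time of their first treatment with TPI 287". For response, the same section also requires that disease has been re-evaluated.

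**Visits.** Section 10, footnote f: a "final visit will be performed approximately 30 days following completion of treatment with FSRT and/or TPI-287", whichever occurs last. Section 5.7 then schedules follow-up at month 3 and every three months. Footnote g says survival, disease status and "adverse events will be collected approximately every 12 weeks beginning after the final visit for period of up to 18 months".

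**Leaving.** Section 5.7: "Patients will be followed for 18 months after first treatment on study or until death, whichever occurs first". Section 7.4 ends adverse event reporting on the last day of participation. For discontinued patients, 5.8 provides follow-up for progression and for treatment-related toxicities and SAEs present at that time. Replacement under 5.8 is optional and covers "Patients who discontinue from the study for reasons unrelated to the study".

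**The concern.** A 3+3 rule works only if *no DLT* means observed and none occurred. Here a patient who leaves the window early, or whose last weeks are not assessed, can be counted the same way as one followed to the end. The error runs in one direction: it lowers the apparent DLT rate and favours escalation. At stake is the primary endpoint, because a level could be cleared, or named the recommended phase 2 dose, on fewer fully observed patients than the 3 or 6 that Table 2 implies. The unvisited stretch also falls in the period that the 8-week hold was introduced to watch, that of delayed CNS toxicity after concurrent drug and radiation.

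**Working it through.** **1. Calendar** (FSRT on D1-5, TPI 287 on D1, D8 and D15; sections 5.6 and 10)
- Window closes: D5 + 56 = D61.
- Final visit, all three doses on schedule: D15 + 30 = D45.
- Next visit: month 3, about D92 (5.7); or D45 + 84 = D129 if footnote g means one interval after the final visit.
- Delayed CNS DLT period (more than 30 days after FSRT): D36-D61, 26 days.
- Part after the last scheduled visit: D46-D61, 16 of 26 days.

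Dose delays would move the final visit later and narrow the gap. A patient stopping TPI 287 after day 1 would have it at D5 + 30 = D35, leaving all 26 days without a visit.

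**2. The plan's own figure.** Section 14.2 gives a maximum of 36 for escalation. Six ascending levels x 6 patients = 36, so the figure reproduces with no allowance for replacement. The product is an inference; 14.2 states only the total.

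**3. Effect on decisions (illustration).** Assumptions: leaving rate q (not in the documents), leaving independent of DLT risk, risk even over D1-61, no replacement, and Table 2's expansion for two or more grade 2 CNS toxicities ignored. Omitting that expansion makes the baseline below an upper bound for this protocol.
- Unseen share u: last seen D45, 16/61 = 0.262; last seen D15, 46/61 = 0.754.
- Apparent rate: p' = p(1 - qu).
- P(clear) = (1-p')^3 + 3p'(1-p')^2 x (1-p')^3.
- Baseline at p = 0.40: 0.216 + 0.432 x 0.216 = 0.309.
- Example, q = 0.10 and u = 0.754: p' = 0.370 and P(clear) = 0.360.

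| | q = 0 | 5% | 10% | 20% |
|---|---|---|---|---|
| Clear a level, p = 0.40 | 30.9% | 31.8-33.4% | 32.7-36.0% | 34.4-41.6% |
| Clear a level, p = 0.33 | 43.4% | 44.3-45.9% | 45.1-48.4% | 46.9-53.5% |
| At most 1 of 6, p = 0.40 | 23.3% | 24.2-25.7% | 25.0-28.3% | 26.7-33.9% |

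Each range runs from last seen D45 to last seen D15.

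**4. Exactly one leaver in the first three**, second cohort fully observed, p = 0.40. Let a = p(1-u).
- P(0 of 3) = (1-p)^2(1-a).
- P(1 of 3) = 2p(1-p)(1-a) + (1-p)^2 a.
- P(clear) = P(0 of 3) + P(1 of 3) x (1-p)^3.
- u = 0.262: 0.254 + 0.445 x 0.216 = 0.350.
- u = 0.754: 0.325 + 0.468 x 0.216 = 0.426.
- Chance of this case, 3q(1-q)^2: 14% at q = 5%, 24% at 10%.

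**The case against.** The plan clearly intends monitoring, and several provisions limit the harm:
- The 8-week hold runs from the last patient's FSRT, so earlier patients at the level are followed longer before the next opens.
- A delayed grade 3 or higher related CNS toxicity at any time holds escalation and adds 3 patients (5.4).
- Related SAEs after 30 days stay reportable (7.5).
- Section 5.9 has stopping language for delayed toxicity.
- The Protocol Monitoring Committee reviews monthly and can suspend the trial (12.2).
- The MTD level is extended to 10 patients to confirm safety (14.2).
- Replacement is allowed where the objective requires it (5.8).
- Life expectancy over 12 weeks is required (3.1), so early leaving may be uncommon.

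A careful team might also apply the usual 3+3 convention of counting only fully observed patients.

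All of this stands and limits the size of the problem. It does not close the gap. The hold lets time pass without requiring an assessment. The CNS hold, SAE reporting, 5.9 and committee review act only on events that someone has observed, and a grade 3 DLT need not be serious. Month-3 visits and the expansion to 10 come after escalation may have moved on. The usual convention is not written down, and 11.1, the only evaluability rule, sets no observation condition.

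A reader might infer that Table 2 makes *entered* its denominator and so directs that early leavers count as DLT-free. The documents do not support that: *entered* belongs to accrual instructions, the table also uses *treated* and bare counts out of 3 or 6, and the level -1 text asks for more than entry. A reader might also take 43% as the expected effect; it applies only when exactly one of the first three leaves, last seen on day 15.

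**Conclusion.** The point holds as an omission in the rules and schedule that should be corrected. Even when the plan is followed exactly, 16 of the 26 delayed CNS DLT days have no scheduled assessment before the next level may open, and no passage ties the DLT-free count to completed observation. This part needs no assumed leaving rate, only on-schedule dosing.

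The numerical effect is modest at low leaving rates: 1 to 5 percentage points on the chance of clearing a level with a true DLT rate of 40% at 5-10% leaving, and 4 to 11 points at 20%. With exactly one leaver in the first three, the chance is 35-43% against 31%. All these figures are illustrative. Undercounting is possible, not certain.

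**What to change.** - **5.4 and Table 2, cross-referenced in 11.1 and 14:** base escalation and MTD decisions on patients who had a DLT in the window or were observed through 8 weeks after FSRT. Keep the all-treated set for safety tables.
- **Section 10:** add a toxicity contact at week 8 after FSRT, and record each patient's DLT status before the next level opens.
- **5.8:** replace, at the same level, every patient who leaves the window unobserved without a DLT. The sponsor must state how those leaving with related toxicity that is not a DLT are counted, so that nobody is neither evaluable nor replaced. Section 6 raises this case: grade 4 neutropenia ends protocol therapy there, but under 5.4 it is a DLT only if it lasts 7 days or more (or is febrile). These passages must be reconciled.
- **Follow-up:** continue toxicity follow-up to week 8 after discontinuation where consent allows, and reconcile 5.7, 5.8, 7.4 and footnote g.
- **14.2:** state whether 36 means evaluable or enrolled patients.

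**Cost:** protocol wording, one contact per patient, and some replacements with delay. If 36 evaluable patients are needed, expected enrolment is 36/(1-q): about 38, 40 or 45 at 5%, 10% or 20% leaving. These are expected values, not maxima; the chance of needing more is about 30%, 37% and 41%.

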6. DOSING DELAYS/DOSE MODIFICATIONS/TREATMENT DISCONTINUATION

Dose Level	TPI 287 Dose
-2	$5 \text{ mg/m}^2/\text{dose}$
-1	$7 \text{ mg/m}^2/\text{dose}$
1	14 mg/m ² /dose
2	28 mg/m ² /dose
3	56 mg/m ² /dose
4	85 mg/m ² /dose
5	113 mg/m ² /dose
6	$127.5 \text{ mg/m}^2/\text{dose}$

Table 3. Dose Levels for Dose Modification of TPI 287

Below are dose modification tables for the following adverse events: nausea, vomiting, diarrhea, neutropenia, and thrombocytopenia:

Table 4. Management of Nausea

Nausea	Management/Next Dose for TPI 287
\leq Grade 1	No change in dose
Grade 2	Hold until \leq Grade 1. Resume at same dose level.
Grade 3	Hold [*] until < Grade 2. Resume at one dose level lower, if indicated. [*]
Grade 4	Off protocol therapy
*Patients requiring a delay of ≥ 2 weeks should go off protocol therapy.	
Recommended management: antiemetics.	

Vomiting	Management/Next Dose for TPI 287	
\leq Grade 1	No change in dose	
Grade 2	Hold until \leq Grade 1. Resume at same dose level.	
Grade 3	Hold [*] until < Grade 2. Resume at one dose level lower, if indicated.	
Grade 4	Off protocol therapy	
*Patients requiring a delay of >2 weeks should go off protocol therapy.		
Recommended management: antiemetics.		

Table 5. Management of Vomiting

Table 6. Management of Diarrhea

Diarrhea	Management/Next Dose for TPI 287	
\leq Grade 1	No change in dose	
Grade 2	Hold until \leq Grade 1. Resume at same dose level.	
Grade 3	Hold [*] until < Grade 2. Resume at one dose level lower, if indicated. [*]	
Grade 4	Off protocol therapy	
*Patients requiring a delay of >2 weeks should go off protocol therapy.		
Recommended management: Loperamide antidiarrheal therapy		
Dosage schedule: 4 mg at first onset, followed by 2 mg with each loose motion until diarrhea-		
free for 12 hours (maximum dosage: 16 mg/24 hours)		
Adjunct anti-diarrheal therapy is permitted and should be recorded when used.		

Table 7. Management of Neutropenia

Neutropenia	Management/Next Dose for TPI 287			
≤ Grade 1	No change in dose			
Grade 2	Hold until \leq Grade 1. Resume at same dose level.			
Grade 3	Hold [*] until < Grade 2. Resume at one dose level lower, if indicated.			
Grade 4	Off protocol therapy			
*Patients requiring a delay of >2 weeks should go off protocol therapy.				
Table 8. Management of Thrombocytopenia				
Thrombocytopenia	nia Management/Next Dose for TPI 287			
\leq Grade 1	No change in dose			
Grade 2	Hold until \leq Grade 1. Resume at same dose level.			

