Grade 3	Hold [*] until < Grade 2. Resume at one dose level lower, if indicated. [*]			
Grade 4	Off protocol therapy			
*Patients requiring a delay of >2 weeks should go off protocol therapy.				

Infusion interruption is required if a subject experiences a hypersensitivity reaction. A \geq Grade 3 hypersensitivity reaction requires discontinuation. A mild-to-moderate hypersensitivity reaction requires that the infusion rate be slowed (half that of the initial attempt) for the remainder of the trial. The infusion is restarted within 1 hour if the mild-to-moderate signs and symptoms resolve or, if the symptoms take longer to resolve, the infusion is not restarted and the next dose is 1 week at the slower rate.

For each patient, a maximum of one (1) dose reduction of TPI 287 will be allowed after which the patient will be discontinued from the study treatment. If, after interruption of treatment and resolution, treatment is resumed at the same dose and the same toxicity reoccurs with the same severity, next treatment re-initiation must resume at the next dose level irrespective of duration.

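### Sections 5.4 and 6 give contradictory dosing instructions for grade 4 toxicity and different delay limits, and neither is said to govern; the effect on the DLT count is narrow

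*Combined protocol and SAP*

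**What the plan says.** Section 5.4 contains a dosing instruction as well as the DLT definition. Its scope is "In the event of the development of any grade 3 or 4 toxicity felt to be at least possibly related to study drug", and its action is "TPI 287 will be held until resolution to grade 1 or baseline assuming that occurs within 15 day window". It gives no start point for the window, no dose for resumption, and no consequence if resolution takes longer.

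Section 6 has a table for each of nausea, vomiting, diarrhea, neutropenia and thrombocytopenia (Tables 4-8). The grade 4 row of each reads "Off protocol therapy". The footnote to Table 4 (nausea) reads "Patients requiring a delay of ≥ 2 weeks should go off protocol therapy"; the footnote to Tables 5-8 reads "Patients requiring a delay of >2 weeks should go off protocol therapy". For hypersensitivity of grade 3 or higher, Sections 5.3 and 6 both discontinue.

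The last paragraph of Section 6 says "a maximum of one (1) dose reduction of TPI 287 will be allowed after which the patient will be discontinued from the study treatment". If the same toxicity then recurs at the same severity after treatment was resumed at the same dose, "next treatment re-initiation must resume at the next dose level irrespective of duration".

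Sections 5.3 and 5.4 both refer the reader to Section 6 for dose modification. Neither says that Section 6 overrides the instruction in 5.4.

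**The concern.** A related grade 4 event falls under two operative instructions that cannot both be followed: hold and wait for resolution, or end treatment. Two investigators could each comply with the protocol and give different amounts of drug after the same event. In a dose-finding study that is first a safety matter. It also touches interpretation, because the toxicity seen at a dose level is read as the toxicity of three weekly doses at that level, in cohorts as small as three patients. The delay limits and the recurrence rule add smaller ambiguities of the same kind.

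**Working it through.** The plan states no figure on this point to reproduce, and no sample-size figure depends on it. The check compares the passages and then asks which 3+3 counts could move.

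**1. Grade 4 instructions, and whether the event is already a DLT (related events)**

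| Event | Section 5.4 | Sections 5.3 and 6 | Already a DLT under 5.4? |
|---|---|---|---|
| Diarrhea, grade 4 | hold | end treatment (Table 6) | yes |
| Thrombocytopenia, grade 4 | hold | end treatment (Table 8) | yes |
| Neutropenia, grade 4 | hold | end treatment (Table 7) | only if it lasts 7 days or more, or is febrile |
| Nausea or vomiting, grade 4 | hold | end treatment (Tables 4, 5) | yes, unless the 48-hour bullet is read as an exception |
| Hypersensitivity, grade 3 or 4 | hold | discontinue | yes |

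Section 5.4 counts DLTs by patient. Where the last column says yes, holding or stopping cannot change that patient's contribution.

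**2. Delay limits**, in whole days, assuming that the 5.4 window and the Section 6 delay start on the same day:

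| Delay | Table 4 (14 or more ends) | Tables 5-8 (more than 14 ends) | 5.4 (within 15) |
|---|---|---|---|
| 13 days | continue | continue | continue |
| 14 days | end | continue | continue |
| 15 days | end | end | continue |
| 16 days | end | end | outside window |

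On this clock the limits differ by one or two days.

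**3. Recurrence rule.** The sentence before it concerns dose reduction, which suggests a lower level. Table 2 uses the same three words for the higher level, in "Enter 3 patients at the next dose level", but about enrolling cohorts. With three doses, a recurrence after same-dose resumption can affect only dose 3. At level 3 (56 mg/m²) the adjacent levels in Table 1 are 28 and 85 mg/m², so cumulative dose would be 2 × 56 + 28 = 140 or 2 × 56 + 85 = 197 mg/m². The closing words on duration are not reconciled with the two-week limit.

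**4. Exposure at stake.** The plan is three doses (days 1, 8 and 15; Section 5.6). After an event following dose 1, stopping gives 1/3 = 33% of the planned drug. Holding and resuming at the same dose gives up to 100%. In mg/m² that is 14 or 42 at level 1, 56 or 168 at level 3, and 127.5 or 382.5 at level 6. Same-dose resumption is an assumption, since 5.4 names no dose.

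**5. Illustration of size.** The chance that a 3+3 escalates is (1 − p)³ + 3p(1 − p)⁵, where p is the DLT risk per patient. Assume equal risk per dose, so the risk from one dose is p₁ = 1 − (1 − p)^(1/3), and let a share q of patients stop after dose 1. The average risk is then (1 − q)p + q·p₁. For p = 0.33, p₁ = 0.125; at q = 10% the average risk is 0.9 × 0.33 + 0.1 × 0.125 = 0.309.

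| p over three doses | q = 0 | q = 5% | q = 10% | q = 20% |
|---|---|---|---|---|
| 0.20 | 70.9% | 72.2% | 73.6% | 76.4% |
| 0.33 | 43.4% | 45.5% | 47.5% | 51.7% |
| 0.40 | 30.9% | 32.9% | 35.0% | 39.4% |

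The documents give neither p nor q. Section 2.2 lists what appears to be neutropenia at 24%, without grade. The list of frequent events for the weekly schedule in Section 7.1.2 omits it, although related terms may split the count.

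**The case against.** The best defence is that Sections 5.3 and 5.4 both send the reader to Section 6, so the specific tables should prevail over a general sentence in the DLT definition. That is a sensible guess, and it softens the conflict. It does not remove it: the 5.4 sentence is itself an instruction, it names grade 4, and no order of precedence is stated.

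Other points stand in part:
- Section 5.4 times resolution and Section 6 times the dose delay, so the limits may run on different clocks.
- The differing sign for nausea could be an underline lost in the PDF text and should be checked in the source file. The 15-day against two-week difference does not depend on it.
- Both rules withhold drug while the toxicity lasts, and TPI 287 precedes FSRT only on day 1, so what is in dispute is the two later single-agent doses.

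Some stronger readings are tempting but unsupported. A reader might infer that one toxicity faces three delay limits; each faces two, 5.4 and its own table. A reader might take the recurrence rule as an escalation, but its context points the other way, and this gap and the sign mismatch lie inside Section 6. A reader might also expect delays to fall at exactly 7 or 14 days; the tables hold until resolution and do not restrict resumption to weekly slots.

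**Conclusion.** The contradiction is real and is in the current text. For five named grade 4 toxicities and for grade 3 or higher hypersensitivity, the protocol gives incompatible instructions and no rule for choosing between them. The difference can reach two of three doses. The delay-limit mismatch is small, and the recurrence rule needs a stated direction.

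It would be going too far to say that every DLT count, or the MTD as such, depends on which section is followed. Most of the affected events are already DLTs, counted once per patient. What remains is patients with a non-DLT event before dose 2 or 3, chiefly grade 4 neutropenia lasting under 7 days without fever. If that is uncommon, the shift is modest: about 2 percentage points in escalation probability at q = 5% and p = 0.33, under the assumptions above.

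Nor does the contradiction by itself explain how a patient with a third of the planned drug can help clear a level. That would happen under Section 6 alone, because Section 11.1 counts patients as evaluable for toxicity from their first treatment, with no minimum exposure, and Section 5.8 describes replacement only for discontinuation unrelated to the study. Reconciling the dosing text would leave this open.

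**What to change.** Reconcile Section 5.3 (hypersensitivity), Section 5.4, Tables 4-8 and the last paragraph of Section 6 so that:
- each toxicity has one grade 4 instruction;
- each has one delay limit, with one start point and one inequality sign;
- the recurrence rule states its direction and how it relates to the delay limit;
- the protocol says which section governs if they differ.

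Which clinical rule to adopt is for the clinical team.

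Separately, state in Section 5.4 or 14.1 how a patient who receives fewer than three full doses without a DLT counts in the 3+3 denominator, and list doses received per patient beside each cohort's DLT count.

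The cost is a wording amendment with IRB approval under Section 12.3. The reconciliation itself changes no sample size. If the denominator rule calls for replacing under-exposed patients, it could add some, and the 36-patient maximum for escalation should then be checked: it equals 6 levels × 6 patients, which leaves no slack if every level is filled.
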